10.1 Pharmacokinetics

10.1.1 PF-07901801 Concentration

Blood samples for the PK analysis of PF-07901801 concentrations will be collected into appropriately labeled tubes for measurement of PF-07901801 concentrations at the times specified in the Schedule of Assessments (Table 28). Instructions for the collection and handling of biological samples will be provided in the laboratory manual or by the sponsor.

All efforts will be made to obtain the samples at the exact nominal time relative to dosing. Collection of samples within the sampling time window specified in the SoA will not be captured as a protocol deviation, as long as the exact time (24 hour clock time) of the collection is noted on the source document and the CRF.

If possible, all blood for PK should be taken from a peripheral vein or from the lumen of a central venous catheter of the contralateral infusion arm on dosing days.

Samples collected for measurement of PF-07901801 concentrations will be analyzed using validated analytical methods in compliance with applicable SOPs.

Samples collected for analyses of PF-07901801 concentrations may also be used to evaluate safety or efficacy aspects related to concerns arising during or after the study or evaluation of the bioanalytical method. These data will be used for internal exploratory purposes and not reported in the clinical study report.

The PK samples must be processed and shipped as indicated in the instructions provided to the investigator site to maintain sample integrity. Any deviations from the PK sample handling procedure (eg, sample collection and processing steps, interim storage or shipping conditions), including any actions taken, must be documented and reported to the sponsor. On a case by case basis, the sponsor may make a determination as to whether sample integrity has been compromised.

10.2 Immunogenicity Assessments

10.2.1 Anti-PF-07901801 Antibody (ADA) and Neutralizing Anti-PF-07901801 Antibody (NAb)

Blood samples will be collected for determination of ADA and NAb for PF-07901801 into appropriately labeled tubes at times specified in the SoA. Instructions for the collection and handling of biological samples will be provided in the laboratory manual. The actual date and time (24 hour clock time) of each sample will be recorded.

Samples collected for determination of ADA and NAb will be analyzed using a validated analytical method in compliance with applicable SOPs. Samples determined to be positive for ADA may be further characterized for NAb.

Samples may also be used for additional characterization of the immune response and/or evaluation of the bioanalytical method, or for other internal exploratory purposes. These data will be used for internal exploratory purposes and not reported in the clinical study report.

The immunogenicity samples must be processed and shipped as indicated in the instructions provided to the investigator site to maintain sample integrity. Any deviations from the immunogenicity sample handling procedure (eg, sample collection and processing steps, interim storage, or shipping conditions), including any actions taken, must be documented and reported to the sponsor. On a case by case basis, the sponsor may make a determination as to whether sample integrity has been compromised.

10.3 Biomarker and Pharmacodynamics Assessments

Unless prohibited by local regulations or ethics committee decision, blood and tumor biospecimens will be collected to analyze DNA, RNA, protein or metabolic biomarkers for achieving study objectives. Specific biomarker and pharmacodynamic analyses may not be performed if emerging data indicate that they would no longer support study objectives. Biomarker and pharmacodynamic analyses may include but are not limited to peripheral CD47 receptor occupancy, serum cytokines, nanostring/RNA sequencing, TCR sequencing, whole exome sequencing/NGS, multiplex immunohistochemistry and immune function assays.

Peripheral Receptor Occupancy samples will only be collected from approximately 12 participants in the expansion cohort (12mg/kg, 24mg/kg or 48mg/kg or their respective DL-1 or DL-2, ie the RP2D).

Refer to Table 32 for the schedule for collection of samples for biomarker/pharmacodynamics analyses and laboratory manual for sample collection, processing and shipping.

11 SCHEDULE OF PROCEDURES AND ASSESSMENTS

The following procedures and assessments will be performed at the indicated timepoints.

Screening Visit (Day -28 to -1)

- Informed consent
- Demographics
- Inclusion and exclusion criteria
- Medical history
- Cancer history
- Complete physical examination
- Vital signs (temperature, blood pressure, pulse rate, respiratory rate, weight), height
- LVEF by transthoracic echocardiogram or MUGA. Per investigator discretion, this can be performed anytime after screening if clinically indicated
- ECOG PS
- Serum chemistry
- Hematology
- Coagulation
- 12-lead ECG
- Serum pregnancy test and counseled on appropriate contraception (female participants of childbearing potential only)

- Radiologic assessment of disease status using CT, MRI or PET/CT; the method used at baseline should be used for the duration of participant participation
- Collection of FFPE/NBF tumor tissue for biomarkers/pharmacodynamics (tumor block preferred; if tumor block is not available, unstained slides are acceptable). Tumor tissue to be collected anytime after signing of informed consent and prior to treatment on Cycle 1 Day 1. Archival tissue from most recent biopsy is acceptable if fresh tissue specimen is not available at screening. The baseline tissue chosen should be the most recently collected specimen before the start of the study therapy and after the most recent systemic therapy

Cycle 1 Day 1

- Complete physical examination
- Vital signs (temperature, blood pressure, pulse rate, respiratory rate, weight)
- ECOG PS
- Serum chemistry (unless previous assessment was performed within previous 72 hours)
- Hematology (unless previous assessment was performed within previous 72 hours)
- Coagulation (unless previous assessment was performed within previous 72 hours)
- 12-lead ECG (unless previous assessment was performed within previous 72 hours)
- Urine or serum pregnancy test (female participants of childbearing potential only) must be performed and be negative prior to treatment and counseled on appropriate contraception
- Administer PLD
- Administer PF-07901801 (12 mg/kg, 24 mg/kg, 48 mg/kg)
- 60-minute observation period after PF-07901801 infusion; vital signs assessed in 30-minute intervals
- Adverse events
- Concomitant medications and procedures
- Blood collection for CA-125
- Blood collection for PF-07901801 concentration
- Blood collection for PLD concentration
- Blood collection for biomarkers/pharmacodynamics
- Blood collection for PF-07901801 anti-drug antibodies

Cycle 1 Day 8

- Brief physical examination
- Vital signs (temperature, blood pressure, pulse rate, respiratory rate)
- Serum chemistry (unless previous assessment was performed within previous 72 hours)
- Hematology (unless previous assessment was performed within previous 72 hours)
- Administer PF-07901801 (12 mg/kg, 24 mg/kg)
- 60-minute observation period after PF-07901801 infusion; vital signs assessed in 30-minute intervals
- Adverse events

- Concomitant medications and procedures
- Blood collection for PF-07901801 concentration
- Blood collection for biomarkers/pharmacodynamics

Cycle 1 Day 15

- Brief physical examination
- Vital signs (temperature, blood pressure, pulse rate, respiratory rate)
- Serum chemistry (unless previous assessment was performed within previous 72 hours)
- Hematology (unless previous assessment was performed within previous 72 hours)
- Administer PF-07901801 (12 mg/kg, 24 mg/kg, 48 mg/kg)
- 60-minute observation period after PF-07901801 infusion; vital signs assessed in 30-minute intervals
- Adverse events
- Concomitant medications and procedures
- Blood collection for PF-07901801 concentration
- Blood collection for biomarkers/pharmacodynamics

Cycle 1 Day 22

- Brief physical examination
- Vital signs (temperature, blood pressure, pulse rate, respiratory rate)
- Serum chemistry (unless previous assessment was performed within previous 72 hours)
- Hematology (unless previous assessment was performed within previous 72 hours)
- Administer PF-07901801 (12 mg/kg, 24 mg/kg)
- 60-minute observation period after PF-07901801 infusion; vital signs assessed in 30-minute intervals
- Adverse events
- Concomitant medications and procedures
- Blood collection for PF-07901801 concentration

Cycle 2 Day 1

- Complete physical examination
- Vital signs (temperature, blood pressure, pulse rate, respiratory rate, weight)
- ECOG PS
- Serum chemistry (unless previous assessment was performed within previous 72 hours)
- Hematology (unless previous assessment was performed within previous 72 hours)
- 12-lead ECG (unless previous assessment was performed within previous 72 hours)
- Urine or serum pregnancy test (female participants of childbearing potential only) must be performed and be negative prior to treatment and counseled on appropriate contraception
- Administer PLD
- Administer PF-07901801 (12 mg/kg, 24 mg/kg, 48 mg/kg)
- Adverse events
- Concomitant medications and procedures

- Blood collection for CA-125
- Blood collection for PF-07901801 concentration
- Blood collection for biomarkers/pharmacodynamics
- Blood collection for PF-07901801 anti-drug antibodies
- Collection of FFPE/NBF tumor tissue for biomarkers/pharmacodynamics (tumor block preferred; if tumor block is not available, unstained slides are acceptable). Target date for tumor tissue collection is Cycle 2 Day 1 but can collected anytime within seven days prior to and up to 14 days after this visit (ie, tumor tissue should be collected within a 21-day window), other times may be acceptable after consultation with sponsor.

Cycle 2 Day 8 (48 mg/kg dose level only)

• Hematology, unless previous assessment was performed within previous 72 hours, may be completed by a local lab.

Cycle 2 Day 15

- Brief physical examination
- Vital signs (temperature, blood pressure, pulse rate, and respiratory rate)
- Serum chemistry (unless previous assessment was performed within previous 72 hours)
- Hematology (unless previous assessment was performed within previous 72 hours)
- Administer PF-07901801 (12 mg/kg, 24 mg/kg, 48 mg/kg)
- Adverse events
- Concomitant medications and procedures
- Blood collection for PF-07901801 concentration
- Blood collection for biomarkers/pharmacodynamics

Cycle 2 Day 15 and Beyond (at any visit)

 FFPE/NBF Tumor biopsies may be collected at response, progression, at the time of any surgical intervention, end of treatment and at investigator's discretion for biomarkers/pharmacodynamics; tumor block preferred; if block is not available, unstained slides are acceptable

Cycle 2 Day 22 (48 mg/kg dose level only)

• Hematology, unless previous assessment was performed within previous 72 hours, may be completed by a local lab.

Cycle 3 Day 1

- Complete physical examination
- Vital signs (temperature, blood pressure, pulse rate, respiratory rate, weight)
- ECOG PS
- Serum chemistry (unless previous assessment was performed within previous 72 hours)

- Hematology (unless previous assessment was performed within previous 72 hours)
- Urine or serum pregnancy test (female participants of childbearing potential only) must be performed and be negative prior to treatment and counseled on appropriate contraception
- 12-lead ECG (unless previous assessment was performed within previous 72 hours)
- Radiologic assessment of disease status (unless performed within previous 7 days)
- Administer PLD
- Administer PF-07901801 (12 mg/kg, 24 mg/kg, 48 mg/kg)
- Adverse events
- Concomitant medications and procedures
- Blood collection for CA-125
- Blood collection for PF-07901801 concentration
- Blood collection for biomarkers/pharmacodynamics
- Blood collection for PF-07901801 anti-drug antibodies

Cycle 3 Day 8 (48 mg/kg dose level only)

• Hematology, unless previous assessment was performed within previous 72 hours, may be completed by a local lab

Cycle 3 Day 15

- Brief physical examination
- Vital signs (temperature, blood pressure, pulse rate, and respiratory rate)
- Serum chemistry (unless previous assessment was performed within previous 72 hours)
- Hematology (unless previous assessment was performed within previous 72 hours)
- Administer PF-07901801 (12 mg/kg, 24 mg/kg, 48 mg/kg)
- Adverse events
- Concomitant medications and procedures
- Blood collection for PF-07901801 concentration
- Blood collection for biomarkers/pharmacodynamics

Cycle 3 Day 22 (48 mg/kg dose level only)

• Hematology, unless previous assessment was performed within previous 72 hours, may be completed by a local lab.

Cycle 4 Day 1

- Complete physical examination
- Vital signs (temperature, blood pressure, pulse rate, respiratory rate, weight)
- ECOG PS
- Serum chemistry (unless previous assessment was performed within previous 72 hours)
- Hematology (unless previous assessment was performed within previous 72 hours)
- 12-lead ECG (unless previous assessment was performed within previous 72 hours)

- Urine or serum pregnancy test (female participants of childbearing potential only) must be performed and be negative prior to treatment and counseled on appropriate contraception
- Administer PLD
- Administer PF-07901801 (12 mg/kg, 24 mg/kg, 48 mg/kg)
- Adverse events
- Concomitant medications and procedures
- Blood collection for CA-125
- Blood collection for PF-07901801 concentration
- Blood collection for PLD concentration
- Blood collection for biomarkers/pharmacodynamics
- Blood collection for PF-07901801 anti-drug antibodies

Cycle 4 Day 15

- Brief physical examination
- Vital signs (temperature, blood pressure, pulse rate, respiratory rate)
- Serum chemistry (unless previous assessment was performed within previous 72 hours)
- Hematology (unless previous assessment was performed within previous 72 hours)
- Administer PF-07901801 (12 mg/kg, 24 mg/kg, 48 mg/kg)
- Adverse events
- Concomitant medications and procedures
- Blood collection for PF-07901801 concentration

Cycle 5 Day 1, Cycle 7 Day 1, Cycle 9 Day 1, etc. (every odd cycle)

- Complete physical examination
- Vital signs (temperature, blood pressure, pulse rate, respiratory rate, weight)
- ECOG PS
- Serum chemistry (unless previous assessment was performed within previous 72 hours)
- Hematology (unless previous assessment was performed within previous 72 hours)
- Urine or serum pregnancy test (female participants of childbearing potential only) must be performed and be negative prior to treatment and counseled on appropriate contraception
- 12-lead ECG (unless previous assessment was performed within previous 72 hours)
- Radiologic assessment of disease status (unless performed within previous seven days)
- Administer PLD
- Administer PF-07901801 (12 mg/kg, 24 mg/kg, 48 mg/kg)
- Adverse events
- Concomitant medications and procedures
- Blood collection for CA-125
- Blood collection for PF-07901801 concentration
- Blood collection for biomarkers/pharmacodynamics
- Blood collection for PF-07901801 anti-drug antibodies

Cycle 5 Day 1, Cycle 9 Day 1, Cycle 13 Day 1, Cycle 17 Day 1, etc. (every fourth cycle)

• Blood collection for biomarkers/pharmacodynamics

Cycle 5 Day 15, Cycle 7 Day 15, Cycle 9 Day 15, etc. (every odd cycle)

- Brief physical examination
- Vital signs (temperature, blood pressure, pulse rate, respiratory rate)
- Serum chemistry (unless previous assessment was performed within previous 72 hours)
- Hematology (unless previous assessment was performed within previous 72 hours)
- Administer PF-07901801 (12 mg/kg, 24 mg/kg, 48 mg/kg)
- Adverse events
- Concomitant medications and procedures
- Blood collection for PF-07901801 concentration

Cycle 6 Day 1, Cycle 8 Day 1, Cycle 10 Day 1, etc. (every even cycle)

- Complete physical examination
- Vital signs (temperature, blood pressure, pulse rate, respiratory rate, weight)
- ECOG PS
- Serum chemistry (unless previous assessment was performed within previous 72 hours)
- Hematology (unless previous assessment was performed within previous 72 hours)
- Urine or serum pregnancy test (female participants of childbearing potential only) must be performed and be negative prior to treatment and counseled on appropriate contraception
- Blood collection for CA-125
- Administer PLD
- Administer PF-07901801 (12 mg/kg, 24 mg/kg, 48 mg/kg)
- Adverse events
- Concomitant medications and procedures

Cycle 6 Day 15, Cycle 8 Day 15, Cycle 10 Day 15, etc. (every even cycle)

- Brief physical examination
- Vital signs (temperature, blood pressure, pulse rate, and respiratory rate)
- Serum chemistry (unless previous assessment was performed within previous 72 hours)
- Hematology (unless previous assessment was performed within previous 72 hours)
- Administer PF-07901801 (12 mg/kg, 24 mg/kg, 48 mg/kg)
- Adverse events
- Concomitant medications and procedures

End-of-Treatment Visit (7 \pm 3 days after last administration of study treatment)

- Complete physical examination
- Vital signs (temperature, blood pressure, pulse rate, respiratory rate, weight)
- Adverse events

- Concomitant medications and procedures
- Blood collection for PF-07901801 concentration
- Blood collection for PF-07901801 anti-drug antibodies

Safety Follow-Up Visit (30 + 5 days after last administration of study treatment or before initiation of subsequent anti-cancer therapy, whichever occurs soonest)

- Complete physical examination
- Vital signs (temperature, blood pressure, pulse rate, respiratory rate, weight)
- ECOG PS
- Serum chemistry (unless performed within previous 72 hours)
- Hematology (unless performed within previous 72 hours)
- 12-lead ECG
- Urine or serum pregnancy test (female participants of childbearing potential only) and counseled on appropriate contraception
- Radiologic assessment of disease status (unless performed within previous 7 days)
- Adverse events
- Concomitant medications and procedures
- Blood collection for CA-125
- Blood collection for PF-07901801 concentration
- Blood collection for PF-07901801 anti-drug antibodies

Long-Term Follow-Up Period

- Radiologic assessment of disease status (participants who have not experienced disease progression)
- Participants with an unresolved AE at the Safety Follow-Up visit considered possibly related to ADA formation may be asked to return to the clinic for ADA blood sampling at approximately 3-month intervals (if feasible given the underlying disease) until the AE or its sequelae resolve or stabilize at a level acceptable to the investigator and sponsor up to a maximum of 12 months.
- Survival and initiation of new anti-cancer therapies (assessed every 12 ± 2 weeks; telephone contact is acceptable)

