After three to six participants in a dose cohort complete the 28-day dose-limiting toxicity assessment period, the incidence of dose-limiting toxicity, treatment-related safety observations and other available data, such as pharmacokinetic data, will be reviewed by the medical monitor, sponsor and investigators. If no participant in a three-participant cohort or no more than one participant in a six-participant dose cohort experiences treatment-related dose-limiting toxicity, the dose level will be deemed safe and dose escalation may proceed unless there are other unsuspected but concerning safety observations that suggest either an expansion of the current dose level or implementation of an intermediate dose level.

Objective disease assessments will be performed after every 8 ± 1 weeks through week 48, or until participant has been on study for one year, and every 12 ± 2 weeks thereafter. Participants who withdraw from the study without objective evidence of disease progression will be followed until documentation of disease progression or initiation of another treatment. All participants will be followed in the Long-Term Follow-Up period for survival.

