9.2.1 PLD Treatment Interruptions

Treatment with PLD may be temporarily suspended for up to 56 days to allow for resolution of adverse events. Dose interruptions for reason(s) other than toxicity and re-treatment may be allowed in accordance with standard of care if the participant is receiving disease control and after discussion with the sponsor medical monitor. In general, if an interruption of more than 56 days is required due to adverse events, PLD will be permanently discontinued; however, if in the judgment of the investigator, the participant is likely to derive disease control from PLD after a hold of more than 56 days, study drug may be re-started with approval of the sponsor medical monitor. Longer interruptions may be acceptable on a participant-by-participant basis at the discretion of the investigator after discussion with the sponsor medical monitor.

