9.2.2 PLD Re-Treatment Guidelines

The laboratory parameters described in Table 21 should be met for re-treatment with PLD (i.e., initiation of a new cycle).

Table 21. Requirements for Re-Treatment with PLD

Parameter	Criterion
ANC	$\geq 1.5 \times 10^9 / L$
Platelet Count	\geq 75 × 10 ⁹ /L
Bilirubin	$\leq 1.5 \times \text{ULN}$ ($\leq 2 \times \text{ULN}$ if hyperbilirubinemia is due to Gilbert's
	syndrome)
AST, ALT	\leq 3 × ULN (<5 × ULN if liver metastases)
Treatment-Related Adverse Event	NCI CTCAE Grade <2 or baseline level (except for alopecia)

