- h. Pregnancy tests will be performed in WOCBP. A serum pregnancy test is required at screening. Following screening, pregnancy tests may be urine or serum tests, and must have a sensitivity of at least 25 mIU/mL. A pregnancy test must be performed and be negative prior to treatment with IP at baseline and at subsequent treatment visits. Participants will also be counseled on the use of appropriate contraceptive methods at these timepoints.
- i. Assessed objectively by CT, MRI or PET/CT; the method used at baseline should be used for the duration of participant participation. Performed every 8 ± 1 week until Week 48 or participant has been on study for one year, and every 12 ± 2 weeks thereafter. CR or PR should be confirmed by repeat assessment at least four weeks after initial observation; treatment can continue during the interval between initial observation and confirmation. In the event that a participant is removed from the study in the absence of radiologic disease progression, a radiologic disease assessment should be performed at the Safety Follow-Up Visit if not performed within the previous four weeks and disease status should be assessed during Long-Term Follow-Up until radiologic demonstration of progression or initiation of new anti-cancer therapy, whichever occurs first

Table 28. Schedule of Assessme	en	m	21	6	P	22	•	A	f	of	e	ηÌ	ł	6	h	cl	S		28	le	ah	T
--------------------------------	----	---	----	---	---	----	---	---	---	----	---	----	---	---	---	----	---	--	----	----	----	---

ACTIVITY	Screening		Cyc	le 1		C	ycle 2	2, Cycl	e 3	Су	cle 4	Subseq	uent	End of	Safety	Long-
		D	ay in	Cycl	e	1	Day i	n Cycl	e	Day i	n Cycle	Cycles 1	Day in	Treatment	Follow-	Term
							(± 3	days)		(± 3	days)	Cyc	ele	Visitz	Up	Follow-Up
												(± 3 d	ays)		Visit ^{aa}	Period
	Day -28 to -	1	8	15	22	1	8	15	22	1	15	1	15			
	1															

- j. PLD should be administered through a free-flowing catheter at 40 mg/m² by intravenous infusion. The initial infusion rate should be 1 mg/min to minimize the risk of infusion reactions. If no infusion-related adverse reactions are observed, the rate of infusion can be increased to complete administration of the drug over one hour in accordance with institutional guidelines. Medications for treatment of infusion-related reaction and CPR equipment must be available before start of treatment; prophylaxis in accordance with institutional guidelines is acceptable

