7.1.2. Secondary Efficacy Outcome Analysis

Duration of response (DOR) will be calculated for participants who achieve a confirmed CR or confirmed PR, and is defined as the time from the date of first documented response (CR or PR) to the date of documented progression or death of any cause after achieving response. Participants who complete or discontinue the study without disease progression or death, as well as participants who receive alternate anti-cancer therapy prior to disease progression, will be censored at their last adequate response assessment date or last adequate assessment prior to the start date of alternate anti-cancer therapy. The number of events and the number of censored participants will be summarized, and the median time to PD or death event (reported in days), its 95% confidence interval (using Brookmeyer-Crowley method), and the 25th and 75th percentiles on the time to event for cohort will be summarized.

Disease Control Rate (DCR) is defined as the percentage of participants who have achieved CR, PR, or SD lasting at least 12 weeks. DCR at any time during the study will be summarized, as per the RECIST assessment method.

Progression Free Survival (PFS) is defined as the time from the first PF-07901801 injection (Cycle 1 Day 1) to PD or death of any cause, whichever is first. Participants who complete or discontinue the study without disease progression or death, as well as participants who receive alternate anti-cancer therapy prior to disease progression, will be censored at their last adequate response assessment date or last adequate assessment prior to the start date of alternate anti-cancer therapy. If date of progression occurs on the same date as the start of new anticancer therapy, the progression will be counted as an event. If there is PD or death after missing 2 planned assessments, the participant will be censored at the last non-PD assessment. Censoring reasons will be summarized in the PFS output.

For participants who do not have an adequate baseline tumor assessment or who do not have any postbaseline tumor assessments, censoring will occur on the date of first dose unless death occurred on or before the time of the second planned tumor assessment in which case the death will be considered an event. Note for participants who died without

Template No.: NVA_TP_CR694 Revision 4 Reference: SOPCR008, WPCR013

Template Effective Date:15Feb2023

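### Protocol Section 11 ties response scans to Day 1 of Cycle 3 and every odd cycle, with no change after week 48, contradicting the calendar schedule in the synopsis, Section 5.1 and Table 28

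*Protocol*

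**What the plan says.** **By cycle.** Protocol Section 11 lists what is done at each visit. The first on-treatment scan is under Cycle 3 Day 1: "Radiologic assessment of disease status (unless performed within previous 7 days". The next block is headed "Cycle 5 Day 1, Cycle 7 Day 1, Cycle 9 Day 1, etc. (every odd cycle" and carries "Radiologic assessment of disease status (unless performed within previous seven days". It has no end date and no change of interval.

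**By calendar.** Section 5.1 says "Objective disease assessments will be performed after every 8 ± 1 weeks through week 48", or until one year on study, and every 12 ± 2 weeks after that. The synopsis agrees. Table 28 footnote i gives the same rule: "Performed every 8 ± 1 week until Week 48" or one year, then 12-weekly.

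**What moves a cycle.** Section 9.2.2 gives laboratory criteria that "should be met for re-treatment with PLD (i.e., initiation of a new cycle", so a new cycle starts with PLD re-treatment. Section 9.2.1 says "Treatment with PLD may be temporarily suspended for up to 56 days to allow for resolution of adverse events".

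**What uses the schedule.** SAP 7.1.2 has two PFS rules that depend on it. One is "If there is PD or death after missing 2 planned assessments, the participant will be censored at the last non-PD assessment". The other applies when there is no post-baseline scan: a death counts as an event only if it falls no later than the second scheduled scan. SAP 5.7 dates progression from the scan that showed it.

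**Safety Follow-Up scan.** Table 28 footnote i waives it if a scan was done in the previous four weeks. Section 11 waives it only if one was done in the previous 7 days.

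**The concern.** Both schedules are current instructions to sites. With long delays, or after week 48, no single set of scans satisfies both. If a site works from the Section 11 visit list, a participant whose cycles slip is scanned on a shifted grid, so the timing of tumour assessment depends on toxicity. Progression dates are scan dates, so PFS and DOR inherit that dependence.

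The SAP's missed-scan censoring rule and its early-death rule both need one fixed schedule to count against. If two are available, the same participant can be an event under one and censored under the other, and the choice would be made at programming in an open-label, investigator-assessed trial.

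**Working it through.** The plan states no figure on this point, so the check is schedule arithmetic. Weeks are counted from Cycle 1 Day 1. This is an assumption, because footnote i names no starting point.

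**1. No delay.** Cycles last 28 days, so Day 1 of Cycle n falls at week 4(n − 1).

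| | To week 48 | After week 48 |
|---|---|---|
| Section 11 | 8, 16, 24, 32, 40, 48 | 56, 64, 72, 80, 88, 96 |
| Footnote i | 8, 16, 24, 32, 40, 48 (± 1) | 60, 72, 84, 96 (± 2) |

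The two coincide through week 48. After that, weeks 56, 64, 80 and 88 lie in no calendar window (58–62, 70–74, 82–86, 94–98). Reading the switch as one year changes nothing, because week 48 is the last 8-weekly scan before week 52.

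**2. Delay of d days before Cycle 3.** A Day 1 scan falls at week 8 + d/7, outside weeks 7–9 once d > 7. Section 11 accepts a scan up to 7 days old, so the earliest scan it allows is at week 7 + d/7, outside once d > 14.

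**3. Direction of the date shift.** Assume exponential PFS, S(t) = 0.5^(t/m). Protocol Section 3.4 cites a 4-month median for PLD, and the SAP month is 30.4167 days, so m = 4 × 30.4167/7 = 17.38 weeks. Compare an 8-weekly grid with the same grid shifted by a delay before Cycle 3, scans on Day 1.

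- 14 days: a progression between week 8k and week 8k + 2 (k ≥ 1) is recorded at 8k + 2 instead of 8k + 8, six weeks earlier. The share is S(8)[1 − S(2)]/[1 − S(8)] = 0.727 × 0.077/0.273 = 20%. The other 80% are recorded two weeks later.
- 28 days: S(8)[1 − S(4)]/[1 − S(8)] = 0.727 × 0.148/0.273 = 39% are recorded four weeks earlier and 61% four weeks later.

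The recorded median is the first scan at which S(t) is at most 0.5. If everyone had the delay and the true median were 4 months, it would move from week 24 (S(16) = 0.53) to week 18 (S(18) = 0.49) for 14 days, to week 20 for 28 days, and stay at week 24 for 56 days. With a 3-month median (m = 13.04 weeks) a 14-day delay moves it from week 16 to week 18. It can go either way.

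**4. Change of PFS status.**

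- *After week 48.* Suppose the last scan is at week 48 and the next, at week 72, shows progression. Under Section 11 weeks 56 and 64 were missed, so PFS is censored at week 48. Under footnote i only week 60 was missed, so it is an event at week 72. The share progressing in between is S(48) − S(72) = 0.148 − 0.057 = 0.091, or 2.27 of 25 (1.40 to 3.29 for medians of 3 to 6 months). At an assumed 5–10% skipping every scan in between, 2.27 × 0.05 to 2.27 × 0.10 gives 0.11 to 0.23 of 25 (0.07 to 0.33 across those medians). This is an upper figure, because the odd-cycle scans apply only on treatment.
- *Before week 48.* To pass two calendar windows between consecutive Section 11 scans, Cycle 5 Day 1 must fall after week 25 (day 175) against nominal day 112. That is a delay of more than 63 days, so at least 64. From Cycle 1 to Cycle 3 the limit is day 119 against day 56, again at least 64.
- *Early death.* A participant who stops in Cycle 2 and dies unscanned at week 14 is an event under footnote i (second scan at week 16). Under Section 11 alone Cycle 5 Day 1 never occurs, so the rule has no date to use.

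**The case against.** The calendar rule appears in three places, and nothing makes Section 11 exclusive. A site following both texts would scan at week 8 ± 1 and again at a delayed Cycle 3 Day 1, which means extra scans rather than late detection. Section 11's own long-term follow-up scan entry gives no interval, so that section already has to be read with Table 28. Other sections also limit delays in particular situations: two weeks for hand-foot syndrome and stomatitis (9.2.7, 9.2.8) and 21 days for toxicity that cannot be attributed to one agent (Table 27). Delays as long as the 56 days in Section 9.2.1 may therefore be uncommon. All of this stands and keeps the effect small. It does not remove the contradiction: after week 48 the texts differ with no delay at all.

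A reader might infer that Section 11 systematically records progression later in participants with more toxicity, and so lengthens PFS. The documents do not support that. On average the shifted grid dates progression slightly later, but a sizeable minority are dated earlier. SAP 7.1.2 reports medians, quartiles and rates rather than means, and the median can move either way. No share of participants with a delay is given, so there is no cohort-level figure.

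A reader might also infer that the SAP leaves its planned assessments undefined. That goes too far. SAP 5.3 sends the reader to Table 28 for visit details, which points to footnote i, and the mention in 7.1.2 of two or more missing assessments refers back to its own censoring rule. What remains is that 5.3 lists visits by cycle without mentioning scans, and 7.1.2 names no schedule.

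**Conclusion.** The contradiction is real and sits in current operative text. Scan timing, and with it the recorded progression date, would depend on dose delays at any site working from Section 11 alone, with no consistent direction. The consequences are limited to PFS and DOR, which are secondary and descriptive. Few participants would change PFS status: about 0.1 to 0.2 of 25 after week 48, plus rare early deaths without a scan or cumulative delays of at least 64 days. Those figures rest on exponential PFS with a 4-month median, weeks counted from Cycle 1 Day 1, and an assumed 5–10% skipping rate that the documents do not give. The rule of six responses in 25 counts responses and does not refer to the scan schedule, so it is unaffected. Severity is low: this is a consistency correction. The Safety Follow-Up waiver is a separate mismatch with no shown effect on the analysis.

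**What to change.** - **Protocol Section 11:** replace the scan entries at Cycle 3 Day 1 and odd-cycle Day 1 with a reference to Table 28 footnote i, timed from Cycle 1 Day 1 regardless of dose delays. The Version 2 summary of changes moved scans from every second cycle to the calendar, so this follows the sponsor's own choice.
- **SAP 7.1.2:** add one sentence stating that planned assessments, including the second one used in the early-death rule, are those of footnote i with its windows. This makes explicit what SAP 5.3 implies.
- **Safety Follow-Up scan:** separately, reconcile the four-week waiver in Table 28 footnote i with the 7-day waiver in Section 11.

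The cost is wording only, and the SAP allows modification before database lock. No scans are added. In weeks 49–100 a participant still on treatment would have 4 scans (60, 72, 84, 96) instead of the 6 in Section 11 (56, 64, 72, 80, 88, 96).
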